7.1.2. Trial Endpoints

Efficacy Endpoints

The efficacy endpoints are defined, as follows:

- Technical Success, defined as a combination of A0 ablations (complete tumor ablation with a surrounding 5 mm margin) and A1 ablations (complete tumor ablation with inadequate margins) based on contrast-enhanced MRI performed up to 7 days following the original ablation procedure.
- Technical Efficacy, defined as a combination of A0 ablations (complete tumor ablation with a surrounding 5 mm margin) and A1 ablations (complete tumor ablation with inadequate margins), based on contrast-enhanced MRI scans at 1 month (+/- 7 days) after the original ablation procedure.
- Local tumor progression (LTP), evaluated at every visit after the ablation of the target tumor(s). LTP describes the appearance of tumor foci at the edge of the ablation zone, after at least one contrast-enhanced follow-up MRI scan has documented adequate ablation and an absence of viable tissue in the target tumor and surrounding ablation margin by using imaging criteria.
- Secondary efficacy rate, defined as the percentage of tumors that have undergone successful repeat ablation following identification of local tumor progression at any time during study follow up.
- Progression-free survival, defined as length of time from the original ablation procedure until any type of disease progression (i.e. local or distant).
- Overall survival measured from the time of the original ablation procedure to the time of death or last follow-up if death has not occurred.

Confidential Page 26 of 61

Safety Endpoint

The safety endpoint is the rate of AEs and SAEs reported at each analysis and cumulatively throughout the entire study period.

Patient Reported Outcomes:

- Pain, as measured by Numeric Pain Rating Scale, before the ablation procedure (measured at Screening Visit), post ablation (within 7 days after ablation]), and at the 1-month follow-up visit.
- Quality of Life, as measured by EORTC QLQ-C30 and liver-specific EORTC QLQ-HCC18, before the ablation procedure (measured at Screening Visit), post ablation (within 7 days after ablation), and at each follow-up visit.

Health Economics:

 Health economics associated with the ablation procedure, including complete procedure time, ablation time, number of ablations, number and types of probes, change in probe position, number of computed tomography (CT) and ultrasound scans performed for probe and margin assessment, and length of hospital stay.

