	Local Tumor Progression and over one missed tumor assessment prior to confirmed	Date of the latest evaluable local tumor assessment prior to the missed	
B2	LTP	assessment	Event
		Date of last local	
		tumor assessment	
	No progression, either alive or	with no documented	
С	death	LTP	Censored

Table 3: Censoring Rules for LTP

		Date of last tumor assessment with no documented	
D	Dead	progression	Censored
		Date of last tumor	
		assessment with no	
		documented	
E	Withdrawal by Subject	progression	Censored

Local tumor progression rates at 3, 6, 9, 12, 18, 24, 30, and 36 months will be estimated using the Kaplan-Meier (K-M) method and 95% confidence intervals (Greenwood's formula) will be provided.

The K-M curve of time to LTP will be provided.

Secondary efficacy rate (the 2nd interim, final)

Secondary efficacy rate is defined as the percentage of subjects whose tumors have undergone successful repeat ablation following identification of local tumor progression at any time during study follow up.

It could be found in CRF page, Ablation Zone Assessment, "Re-ablate with Neuwave". For subgroup that has LTP and used Certus to re-ablate, the number and percentage of subjects achieving secondary efficacy, will be summarized and a 95% confidence interval will be estimated using wald method.

Progression-free survival (PFS) (the 2nd interim, final)

PFS is defined as length of time from initial ablation until disease progression.

Table	e 4. Censoring Rules for PFS		
	Situation	Event Date	Outcome
No po	st-baseline or no baseline Ablation Zo	ne Assessment	
	No post-baseline tumor evaluation		
A1	and alive	Date Ablation performed	Censored
	No post-baseline tumor evaluation		
	but died on or before the second		
A2	scheduled tumor assessment	Date Ablation performed	Censored
With baseline and post-baseline tumor assessments			

Table 4: Censoring Rules for PFS

В	Any Tumor Progression and zero or one missed tumor assessment prior to progression	Date of first progression	Event
		Date of last progression	
	PD happens after >=2 consecutively	assessment before	
С	missing tumor assessment	missing assessments	Censored
		Date of last progression	
		assessment with no	
D	No progression	documented progression	Censored

Progression-Free Survival rate will be estimated using the Kaplan-Meier method and 95% confidence intervals (Greenwood's formula) will be provided for 6, 12, 18, 24, 30, 36 months.

The K-M curve of time to progression will be provided.

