Progression-free survival (PFS) sensitivity analysis (the 2nd interim, final)

PFS is defined as length of time from initial ablation until disease progression or death, whichever comes first.

Overall survival (OS)

36-month OS is measured from the time of the first ablation procedure to the time of death or last follow-up, if death has not occurred.

For OS, death from any cause will be considered as an event. If no death is reported, then use the cut-off date as the censored date of OS.

Overall Survival rate will be estimated using the Kaplan-Meier method and 95% confidence intervals (Greenwood's formula) will be provided.

The K-M curve of time to death will be provided.

Quality of Life (QoL)

EORTC QLQ-C30

The EORTC QLQ-C30 (version 3.0) comprises 30 questions and provides a multidimensional assessment of QoL. The QLQ-C30 is composed of both multi-item scales and single-item measures. EORTC QLQ-C30 can be combined to produce 5 functional scales (Physical, Role, Cognitive, Emotional, and Social), 3 symptom scales (Fatigue, Pain, and Nausea/vomiting), 5 individual items (dyspnea, insomnia, appetite loss, constipation, and diarrhea) and a global measure of health status. Each of the multi-item scales includes a different set of items - no item occurs in more than one scale. All of the scales and single-item measures range in score from 0 to 100. A high scale score represents a higher response level.

There are four items for each question (from Q1 to Q28): from not at all, a little, quite a bit, to very much, each will be considered as from 1 to 4. For Q29 and Q30, will be scored from 1 to 7.

No response (NR) will not be considered as missing and not included in the analysis.

Scale	Number of items	ltem range*	Item numbers
Global health status / QoL			
Global health status/QoL	2	6	29, 30
Functional scales			
Physical functioning	5	3	1 to 5
Role functioning	2	3	6, 7
Emotional functioning	4	3	21 to 24
Cognitive functioning	2	3	20, 25
Social functioning	2	3	26, 27
Symptom scales / items			
Fatigue	3	3	10, 12, 18
Nausea and vomiting	2	3	14, 15
Pain	2	3	9, 19
Dyspnoea	1	3	8
Insomnia	1	3	11
Appetite loss	1	3	13
Constipation	1	3	16
Diarrhoea	1	3	17
Financial difficulties	1	3	28

Table 5: Scoring the EORTC QLQ-C30 version 3.0

* *Item range* is the difference between the possible maximum and the minimum response to individual items; most items take values from 1 to 4, giving *range* = 3.

The scoring procedure is as follows:

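### The main PFS analysis counts no death as an event, and SAP Tables 3 and 4 give opposite outcomes for a local progression found after two missed scans

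*SAP*

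**What the plan says.** **Main PFS.** SAP 8.4.1: "PFS is defined as length of time from initial ablation until disease progression". Table 4 has one event row, B: "Any Tumor Progression and zero or one missed tumor assessment prior to progression". Row A2, the only row that names death, covers a patient with no scan after ablation "but died on or before the second" scheduled assessment. That patient is censored at the ablation date, exactly as row A1 treats a living patient. A death after a clean scan has no row of its own and falls under row D (no progression), censored at the last clean assessment. The SAP adds: "The K-M curve of time to progression will be provided".

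**Sensitivity analysis.** Also under the name PFS, at the second interim and final analyses: "PFS is defined as length of time from initial ablation until disease progression or death, whichever comes first". It has no event or censoring table.

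**Protocol.** Section 7.1.2: "Progression-free survival, defined as length of time from the original ablation procedure until any type of disease progression (i.e. local or distant". The definition recurs in the Synopsis and in sections 3.2, 7.1.6 and 7.2.2. None of these names death.

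**Missed scans.** Table 3 row B2 (LTP) covers "Local Tumor Progression and over one missed tumor assessment prior to confirmed" LTP and makes it an event, dated at the latest evaluable assessment before the gap. Table 4 row C (PFS) applies when "PD happens after >=2 consecutively" missing assessments, and censors at the last assessment before the gap.

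**The concern.** An endpoint whose name promises survival without progression treats death as uninformative censoring. Two different quantities will be reported as PFS, and the one that ignores death is the main one. Read as progression-free survival, it is too high whenever a patient dies before progressing.

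The two tables also contradict each other. Protocol 7.1.2 includes local progression in PFS, and section 7.2.4 asks the physician to say whether a progression is of the original target tumour. The same finding can therefore count as a local progression and not as a progression. Row C again pushes PFS upward.

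The trial tests no hypothesis, and protocol 8.4 bases acceptability on an overall reading of the data against other HCC treatments. The descriptive estimates are the evidence, so what they measure has to be clear.

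**Working it through.** **1. Plan's own figure.** Neither document gives a PFS rate, event count or power. The sample size reproduces: 100/(1 − 0.20) = 125; 125 + 12 run-in patients = 137. The point does not affect it.

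**2. Outcome of each case under Table 4.**

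| Patient | Row | Outcome |
|---|---|---|
| Progression, at most one scan missed before it | B | Event |
| Progression after two or more consecutive missed scans | C | Censored |
| No scan after ablation, early death | A2 | Censored at ablation |
| Clean scan, then death | D | Censored at last clean scan |
| No scan after ablation, death after the second scheduled assessment | none | Not stated |
| Progression after two or more non-consecutive missed scans | none | Not stated |

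**3. Size of the death effect (illustration).** The cited Chinese series of 1007 patients (protocol 4.1.1) had 72.5% overall survival at 3 years. Expected deaths among 125: 125 × 0.275 = 34.4. The share of deaths that precede progression is assumed to be 10%, 25% or 50%, that is 3.4, 8.6 or 17.2 patients. Let S be the main 36-month figure.

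- Method A, share of deaths: h1 = −ln(S)/36. Solve h2/(h1+h2) × (1 − exp(−36(h1+h2))) = share × 0.275 for h2. The composite is exp(−36(h1+h2)). For S = 0.50 and share 0.50: h1 = 0.01925, h2 = 0.00580, composite = exp(−0.902) = 0.406.
- Method B, share of the death hazard: composite = S × 0.725^share. For S = 0.50 and share 0.50: 0.50 × 0.851 = 0.426.

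| Main figure S | Method A: 10% / 25% / 50% | Method B: 10% / 25% / 50% |
|---|---|---|
| 30% | 28.6 / 26.5 / 23.1 | 29.1 / 27.7 / 25.5 |
| 50% | 48.1 / 45.3 / 40.6 | 48.4 / 46.1 / 42.6 |
| 70% | 67.7 / 64.3 / 58.6 | 67.8 / 64.6 / 59.6 |

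The gap is 1.6 to 9.4 points at S = 50%, and about 0.9 to 11.4 points over the whole table. For scale, the 95% CI half-width at 50% is 1.96 × √(0.25/125) = 8.8 points, or 9.8 points with 100 patients.

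**4. The two tables on one patient.** Scans are clean at months 1, 3 and 6 and missed at months 9 and 12; local progression is seen at month 18. Table 3 B2 gives an LTP event at month 6. Table 4 C gives PFS censored at month 6: same date, opposite outcome. With k such patients among 125 and no other events or censoring by month 6, freedom from LTP is 1 − k/125: 99.2% for k = 1 and 97.6% for k = 3. PFS stays at 100%. Estimated PFS can thus exceed freedom from one of its own components.

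**5. Size of the missed-scan effect (illustration).** I simulated 1,000,000 patients per setting, with scans on the protocol schedule, each missed independently, and true 36-month progression of 50%. Row C was applied when two or more scans immediately before the detecting scan were missed.

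| Scans missed | Patients in row C | Of 125 | Rise in 36-month PFS |
|---|---|---|---|
| 5% | 0.3% | 0.4 | 0.1 points |
| 10% | 1.1% | 1.4 | 0.7 points |
| 20% | about 4.1% | 5.2 | 2.3 points |

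For patients with an LTP event but no PFS event, I took the cited LTP rate of 5.9% over a mean of 17.3 months as a constant hazard (0.059/17.3 per month). This gives 0.1, 0.3 or 1.2 of 125 patients. The 5.9% is per lesion (78/1363). Using 78/1007 as an upper bound per patient gives 0.1, 0.4 or 1.5.

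**The case against.** The strongest reply is that nothing is lost. The composite is pre-specified at the same two analyses as the main PFS, overall survival is reported, and no hypothesis or threshold depends on PFS, which is one of six unranked efficacy endpoints. The SAP follows its protocol and labels the curve as time to progression, so the gap is a difference between two quantities and not a bias in the one defined. The documents name no PFS comparator. The missed-scan conflict touches very few patients.

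Much of this stands. It rules out any claim of a wrong decision or a wrong sample size, and it is right that the naming problem starts in the protocol. The illustration has limits too: the upper end assumes that half of deaths precede progression, and the cited survival comes from treatment-naive lesions while this trial also admits recurrent HCC.

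It does not remove the point. Two different estimates would still carry the name PFS, with the more favourable one as the main result. The composite still lacks an event table, and Table 4 cannot serve it unchanged because it censors deaths. The ordinary reading is Table 4 with death added as an event, but protocol 8.6 gives other censoring dates: database lock at an interim, last known visit at the final analysis. The conflict between Tables 3 and 4 is a contradiction at any frequency.

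**Conclusion.** The concern holds on both counts, and should be fixed. The main analysis called PFS is time to progression, in the SAP and in the protocol definition it follows. Tables 3 and 4 assign opposite outcomes to the same local progression after two consecutive missed scans. These conclusions rest on the text alone.

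The sizes rest on assumptions, because the documents give no rate of progression, of death before progression or of missed scans. The death effect could be about as large as the sampling error of the estimate. The missed-scan effect is small unless missed scans are common. Both raise the main PFS. Significance level, power, sample size and stopping are untouched.

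**What to change.** Amend the SAP as follows.

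1. Define the main PFS as the time to progression or death from any cause, whichever is earlier, with death as an event row in its censoring table. Relabel the present analysis as time to progression and keep it as supportive, so that the quantity the protocol now defines is still reported.
2. Put one missed-scan rule, identically worded, in Tables 3 and 4, and let it cover non-consecutive misses. Counting the progression as an event in both is preferable, with the other dating or censoring as a sensitivity analysis. Censoring in both would also remove the contradiction.
3. Add a sentence giving the composite's censoring date and how it relates to protocol 8.6.
4. Note the difference from the protocol definition, and align its five statements at the next amendment.

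The cost is SAP text only, and protocol 8.7 allows changes through an amended SAP. Deaths already have a CRF page (SAP 8.5.2), so no new data are needed. The downsides are a less favourable main PFS figure and a documented mismatch with the protocol until it is amended.

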Adverse event: The AE or SAE may not cause the patients to discontinue the study. If the investigator decides to withdraw a patient from the study, this patient must be followed up, until the AE is resolved or until the stable clinical endpoint is reached;

Death: The cause of death will be documented.

Lost-to-follow-up: All patients should be able to participate in all scheduled clinical follow-ups, providing the appropriate contact information. If a patient can't return to undergo the scheduled

Confidential Page 29 of 61

clinical visit, attempts to contact the patient by phone should be done for 3 times to ask the patient to participate in all scheduled clinical follow-ups. Each attempt to contact should be recorded in the source document. If the patient makes no response to all three times of telephone contact, the investigator must send a registered mail to the patient. If the patient makes no response to the registered mail and makes no further contact, the patient is considered lost-to-follow-up and the respective eCRF will be completed.

Procedure for Patient's Discontinuation from the Study:

The patients must return for all follow-up visits as specified at the end of the synopsis in Table 1: Schedule of Activities. If the patient is withdrawn from the study early, the reasons for termination will be documented in the source document and site files and submitted via the eCRF.

Patients withdrawn from the study early will be included in the analysis of results, however, no new patients will be recruited to replace the patients withdrawn from the study as a 20% attrition rate has already been considered in the current sample size.

4) Enrollment

Patients will be considered enrolled into the study upon satisfaction of the following criteria:

- Completion of the informed consent process.
- It is determined by the investigator that the patient meets all inclusion criteria and does not meet any exclusion criteria.

No procedures related to the study and which are not SOC should be conducted prior to signing the informed consent.

5) Expected overall duration of clinical trial and reasons for determination

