8.5. Criteria and Reason for Terminating the Trial based on the Statistical Results

There are no planned analyses whose intent would be to stop the study early due to futility or superiority.

8.6. Statistical Method of All Data, together with the Handling Method of Missing, Unused and Error Data (including Termination and Withdrawal Halfway) and Unreasonable Data

All analyses will be performed only on patients undergoing ablation with the NeuWave Microwave Ablation System and only observed data will be analyzed. There will be no imputation of missing data for any parameters or for early terminated patients. At a given interim analysis time point, if a patient has not discontinued from the study, then the patient will be considered censored as of the date of the interim database lock for that analysis unless they have had an occurrence of the given endpoint prior to that interim database lock date. For time to event endpoints in the final analysis of data, patients who have not experienced an event will be considered censored at the last known visit date.

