8.1.5 Last Contact Date

The last contact date will be derived for subjects not known to have died at the analysis cut-off date using the latest date among the following applicable or available data:

- All visit dates, including examination/scan dates (e.g. laboratory, vital signs, NPRS pain, EORTC QLQ- HCC 18/C 30, ECG, ECOG, tumor imaging scan, tumor assessment)
- Medication/procedure dates (including ablation, concomitant medications/surgeries, therapies/procedures administered after study treatment discontinuation, etc.)
- Adverse event start and end dates

- Dates of protocol deviations
- Date of trial completion/discontinuation in [CRF form Subject Completion/Discontinuation]

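### The SAP censors overall survival at the cut-off date even for withdrawn or lost subjects, which contradicts its own OS definition and protocol 8.6 and can overstate 36-month OS

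*SAP*

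**What the plan says.** The OS part of SAP 8.4.1 holds two statements that do not agree. The definition measures OS from the first ablation "to the time of death or last follow-up, if death has not occurred". The next paragraph says "If no death is reported, then use the cut-off date as the censored date of OS", which covers every subject without a reported death, including those who have left the study.

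Protocol 8.6 sets the censoring rule for time-to-event endpoints. In the final analysis, "patients who have not experienced an event will be considered censored at the last known visit date". The database-lock date is allowed only at an interim, and only for patients still in the study: "if a patient has not discontinued from the study, then the patient will be considered censored as of the date of the interim database" lock.

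SAP 8.1.5 has a separate concept: "The last contact date will be derived for subjects not known to have died at the analysis cut-off date". The OS rule does not refer to it. For local tumor progression (LTP), SAP Table 3 has its own row for "Withdrawal by Subject", censored at the last tumor assessment.

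**The concern.** A subject who withdraws at month 6 and is never heard from again would stay in the OS risk set until the cut-off and count as alive throughout. If that subject dies at month 20 and no one reports it, the death is lost and the curve stays up. The direction is always in the device's favor.

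The plan describes no systematic survival tracing after withdrawal or loss. Protocol 7.1.5 requires phone calls and a registered letter before a patient is declared lost. For a patient withdrawn because of an adverse event, it says "this patient must be followed up, until the AE is resolved or until the stable clinical endpoint is reached". These steps, and the Death CRF page in SAP 8.5.2, may pick up some later deaths but not all.

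The study has no control arm and no acceptance criterion. Protocol 8.4 judges the device by setting all the data beside other HCC therapies, so an OS rate based on unobserved time would weaken that comparison.

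**Working it through.** **Text comparison.**

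| Situation | SAP 8.4.1, OS rule | SAP 8.4.1, OS definition | Protocol 8.6 |
|---|---|---|---|
| Final analysis, no reported death | Cut-off date | Last follow-up | Last known visit |
| Interim, still in study | Cut-off date | Last follow-up | Database-lock date |
| Interim, discontinued | Cut-off date | Last follow-up | Lock date not allowed |

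The conflict with the protocol therefore concerns discontinued or lost subjects at any analysis, and the last-visit rule at the final analysis. For ongoing patients at an interim the rule agrees with the protocol. Subjects who complete 36 months are almost unaffected, because their cut-off falls at about 36 months or later.

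**Inputs.**
- Non-run-in n: 100 / (1 − 0.20) = 125, and 125 + 3 × 4 = 137, as in protocol 8.2.1 and SAP 7.
- Dropout p: 20% (protocol 8.2.1 and 8.3), with 10% and 5% as assumed lower values.
- True 36-month OS: 72.5%, the 3-year figure cited in protocol 4.1.1, used as an illustration.
- Assumed: exponential survival, non-informative dropout, no post-dropout death reported.

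The documents state no OS target, so there is no OS figure of the plan to reproduce.

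**Bias.** The hazard is λ = −ln(0.725)/36 = 0.00893 per month. Under the SAP rule the estimate tends to 1 minus the probability of dying by month 36 and before dropout, so

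bias = p × [mean of S(u) over the loss time u − S(36)].

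For losses uniform over 0 to W months, the mean of S(u) is (1 − e^(−λW))/(λW).
- W = 36: mean 0.8551, difference 0.1301.
- W = 12: mean 0.9483, difference 0.2233.

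| Dropout | Losses over 36 months | Losses within 12 months |
|---|---|---|
| 20% | 75.1% (+2.6 points) | 77.0% (+4.5) |
| 10% | 73.8% (+1.3) | 74.7% (+2.2) |
| 5% | 73.2% (+0.7) | 73.6% (+1.1) |

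Exponential dropout reaching 20% by month 36 gives 75.2%. If a share a of the later deaths is reported, the bias is multiplied by (1 − a). With half reported, the 20% row becomes +1.3 to +2.2 points; with all reported it is zero.

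**Interval.** The 95% half-width at n = 125 and 20% dropout is 1.96 × the asymptotic Greenwood standard error.
- Rule: 1.96 × √[Ŝ(1 − Ŝ)/125] = 7.6 points (losses over 36 months) or 7.4 (within 12).
- Censoring at loss: 1.96 × S(36) × √[(1/125) ∫₀³⁶ λ/(S(t)G(t)) dt], where G is the share not yet lost. This gives 8.3 or 8.6 points.

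In simulation with 20% dropout and no later deaths reported, coverage of the 95% interval fell to about 0.89 (losses over 36 months) and 0.76 (within 12 months).

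**Informative dropout.** Suppose the 20% who drop out (losses over 36 months) die at 2 or 3 times the hazard of the others, with overall OS held at 72.5%. The rule gives 76.3% or 77.0%, and last-contact censoring gives 74.1% or 75.1%. The rule itself adds 2.2 or 2.0 points. The remainder is informative censoring, which no choice of censoring date removes.

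**The case against.** Protocol 8.7 allows a final or amended SAP to change planned analyses, so a departure from 8.6 is not in itself a breach. That is correct, but the SAP does not present this as a change, and 8.7 does not resolve the contradiction inside the SAP.

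The sentence may be a slip. SAP 8.1.5 derives a last contact date with no other stated use, and survival censoring is its natural purpose. That is plausible, and the bias arises only on the literal reading. A programmer would still have to guess.

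OS may not be planned at the interims: unlike LTP and PFS it carries no interim tag, and SAP 8.6 does not list it. This is fair. The final analysis is where the conflict is certain.

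The upper figure is a corner case. The 20% is an upper limit tied to one-year data, and protocol 10.1 counts death among the reasons for discontinuation. If 20% is all-cause attrition at one year and 1-year OS is the cited 91.2%, non-death loss is about 20 − 8.8 = 11.2%. Early losses at that rate give 0.112 × 22.3 = +2.5 points. This stands: +4.5 should not be read as typical, and biases of 1.3 to 2.6 points lie well inside a half-width of about 8.

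Not all of the narrowing comes from the inflated risk set. Full follow-up at 72.5% would give 7.8 points, so part of the drop to 7.6 or 7.4 reflects the higher point estimate. The LTP comparison is also limited, since LTP is read on MRI. Both points change emphasis only.

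**Conclusion.** The concern holds. The OS censoring sentence contradicts the definition it is meant to implement and protocol 8.6, and read literally it can only push 36-month OS upward.

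With 5% to 20% dropout and no later deaths reported, the overstatement is 0.7 to 4.5 points around a true value of 72.5%. It shrinks in proportion to the share of later deaths that are reported. Confidence is high on the textual conflict and the direction. The size rests on an assumed loss rate, loss timing and true OS that the documents do not settle. OS is one of six descriptive efficacy endpoints, so no test, sample size or stopping decision changes. The point should be fixed before the final OS analysis is programmed.

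**What to change.** Replace the sentence in SAP 8.4.1 with wording such as: *Subjects without a reported death are censored at the last date on which they were known to be alive, not later than the cut-off date. If OS is reported at an interim analysis, subjects who have not discontinued are censored at the database-lock date, as in protocol 8.6.*

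Take the date from the sources in SAP 8.1.5, but only those that show the subject was alive. Listed sources such as "Dates of protocol deviations" do not, and the date on the discontinuation form needs review for the same reason. The SAP should name the qualifying sources.

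The last date known alive is not identical to the protocol's last known visit date, so the two must be reconciled: either adopt the visit date for OS, or record the choice as a change under protocol 8.7.

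The cost is a short text change, a decision on which dates qualify, and that reconciliation. The contact dates are already collected. Reported OS may come out slightly lower and its interval slightly wider. Informative censoring would remain and should be acknowledged when OS is reported.
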